These trials, however, were limited by the fact that a majority of the patients were already using these treatments that they had to discontinue and enter a run-in period before randomisation, which does not emulate the clinical setting. Moreover, the trials represent a limited view of the patients who could potentially use these treatments, with several exclusion criteria involving for example stage of disease, lung function and exacerbation history, in addition to the exclusions of many patients during the screening and run-in periods. Thus, a real-world study of patients who are representative of clinical practice is of interest. Finally, assessing the effectiveness in terms of COPD exacerbations should be balanced against the safety of ICS with respect to pneumonia in the context of real-world clinical practice.

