propensity score-matched approach. The potential comparator subjects will be selected from the base cohort by forming time-based exposure sets defined by the calendar year of entry into the base cohort for the LABA-TIO and LABA-ICS simultaneous prescription users. To allow matching on the propensity of treatment choice, we will compute high-dimensional time-conditional propensity scores (TCPS) by identifying all available data (e.g., diagnoses, procedures, medications) in the one-year period prior to the date of cohort entry for each time-based exposure set using Cox proportional hazards regression. Then, for each LABA-TIO exposed subject, and starting chronologically with the first one, we will identify a matched comparator subject from the members of the subject's time-based exposure set. We will first match subjects on sex, previous components of the study treatment (LABA only, TIO only, ICS alone, none of these) and the presence of an acute COPD exacerbation in the year before cohort entry. The matched reference subject will then be selected as the one with the closest time-conditional propensity score in the matched set, after trimming within each exposure set, and allowing a maximum difference in scores of 0.05 for a match. In the absence of a tight propensity score match, we will take the closest and the analysis will be complemented by an adjustment for the propensity score.

After matching, the subjects in the study cohort will be followed up for up to one year from cohort entry (the date of the matched set), with follow-up ending at the earliest of the date of a switch or addition of either an ICS for the LABA-TIO group or of tiotropium to the LABA-ICS group, death, one year after cohort entry, December 31, 2016, or the end of coverage in the practice, whichever occurs first.

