7.7 STUDY SIZE

In our previous study of the cardiovascular effects of long-acting bronchodilators, there were around 230,000 users of LABA or TIO between 2002 and 2012 in the CPRD, which should include around 140,000 who come from HES-linked practices [P16-10095]. From these, we expect around 4,000 who received a LABA and tiotropium on the same day, where the LABA is not combined with an inhaled corticosteroid in a single inhaler. The number of users of LABA-ICS is over 100,000, providing a large pool for matching purposes. Thus, after matching and trimming, we expect the study to include a minimum of 3,000 patients per arm, a conservative estimate. Using recent data from the FLAME trial [P16-05628], we expect that the cumulative incidence of a first COPD exacerbation, moderate or severe,

during the one-year follow-up is expected to be 50%. These sample sizes will permit to detect a 15% reduction in the risk of a first exacerbation (hazard ratio 0.85) with 99% power and a 10% reduction (hazard ratio 0.90) with 97% power. For the severe exacerbations, we expect the one-year cumulative incidence to be around 15%, which will permit to detect a 20% reduction in the risk of a first severe exacerbation (hazard ratio 0.80) with 92% power.

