7.9 DATA ANALYSIS

7.9.1 MAIN ANALYSIS

For the base cohort, patient characteristics at baseline will be described using standard descriptive statistics. The unmatched study cohort, which will also address the tertiary objective, will be used to provide and compare baseline patient characteristics between the two groups. These comparisons will also be provided for the matched cohort.

For the analysis of the primary objective, the matched cohort will be used to estimate the crude 1-year cumulative incidence of severe and moderate COPD exacerbations for the two combination treatment groups. The main comparative analysis will also be based on the matched cohort and a time-dependent Cox proportional hazard regression model to perform an as-treated analysis that assesses the effect of current use of LABA-TIO combination versus the LABA-ICS combination on the risk of a first COPD exacerbation. It will provide an estimate of the hazard ratio (HR) of a COPD exacerbation associated with LABA-TIO use relative to LABA-ICS use, along with 95% confidence intervals (CI). Current use will be defined as a prescription dispensed within the 60-day period of the date defined by the risk set of the Cox model. This approach allows consideration of exposure as time-dependent, accounting for the changes in exposure during the follow-up. In particular, this analysis

censors patients stopping one or both of the drugs prior to the index date. Besides the matching inherent in the design, the Cox proportional hazard regression model will be adjusted for additional confounders. This model will include patient characteristics found to be different after matching on propensity scores, as well as the decile of propensity score. Body mass index (BMI) is expected to be the only variable with missing data in the CPRD, though infrequently (less than 4% of subjects in our previous studies in COPD). Patients with missing BMI will be classified as a separate category.

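### The 97% power for HR 0.90 is about 81–82% under the planned Cox analysis even with complete follow-up, and Section 7.7 makes no allowance for as-treated censoring

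*Combined protocol and SAP*

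**What the plan says.** Section 7.7 (Study size) plans for "we expect the study to include a minimum of 3,000 patients per arm, a conservative estimate". For the primary outcome it takes its one-year rate from a randomised trial ("Using recent data from the FLAME trial [P16-05628], we expect that the cumulative incidence of a first COPD exacerbation"). The value used, which covers both grades of event together, "during the one-year follow-up is expected to be 50" percent. From this it states 99% power for HR 0.85 and 97% for HR 0.90. For severe exacerbations it takes an incidence of about 15%, with no source named, and ends with "hazard ratio 0.80) with 92% power". It does not state alpha, sidedness or the formula, or whether the incidences are pooled or those of the comparator arm.

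Section 7.9.1 (Main analysis) specifies an as-treated, time-dependent Cox model with a 60-day current-use window, which "censors patients stopping one or both of the drugs prior to the index date". Section 7.3 (Subjects) also truncates observation, "with follow-up ending at the earliest of the date of a switch or addition" of the other treatment, and at death or end of practice coverage. The documents give no rate for any of these.

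**The concern.** Power for a Cox comparison depends on the hazard ratio and on the number of events that enter the analysis. Section 7.7 appears to depart from this in two ways. One of its three figures does not agree with the hazard ratio beside it. All three use full-year incidence, although the main analysis counts events only while the assigned combination is current. Every patient censored before one year without an event lowers the count, so the direction is certain even though the size is not.

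At stake is how an inconclusive result would be read. Against 97% power, a null finding looks like strong evidence that a 10% reduction has been excluded. Against 70–80% power it does not.

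**Working it through.** **Inputs.** 3,000 per arm, incidences of 50% and 15%, and HRs of 0.85, 0.90 and 0.80 (Section 7.7). Two-sided 5% is an assumption, taken from the 95% confidence intervals in Section 7.9.1.

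**1. Reproduce the stated powers as two proportions**, with the quoted ratio applied to the one-year risk. Power = Φ(|p1 − p2| / √{[p1(1 − p1) + p2(1 − p2)]/3,000} − 1.96).

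- 50% vs 42.5%: 0.075/0.01284 = 5.84; power 99.99% (stated 99%).
- 50% vs 45%: 0.05/0.01288 = 3.88; power 97.3% (stated 97%).
- 15% vs 12%: 0.03/0.00881 = 3.40; power 92.5% (stated 92%).

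**2. Reproduce them as hazard ratios.** Schoenfeld, 1:1: power = Φ(√(E/4) × |ln HR| − 1.96), where E is total events. With pooled incidence and full follow-up, E = 6,000 × 0.50 = 3,000 or 6,000 × 0.15 = 900.

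- HR 0.85: √750 × 0.1625 = 4.45; power 99.4%. Agrees.
- HR 0.80, severe: √225 × 0.2231 = 3.35; power 91.7%. Agrees.
- HR 0.90: √750 × 0.1054 = 2.89; power 82.3%. Does not agree with 97%.

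If the 50% is the comparator arm's incidence, E is 2,892 and HR 0.90 power is 80.9%. A one-sided 5% test gives 89.3%. At HR 0.90, 97% power needs E = 4 × (1.960 + 1.881)²/0.1054² ≈ 5,316 events, out of 6,000 patients. The reason for the gap is that, under proportional hazards, 50% vs 45% is HR = ln(0.55)/ln(0.50) = 0.86, not 0.90.

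**3. Add as-treated censoring.** Let s be the share still on treatment at one year in the absence of an event (assumed). With exponential event and censoring times, λ = −ln(1 − p) and c = −ln(s), the share with a counted event is λ/(λ + c) × [1 − exp(−(λ + c))]. For p = 0.50 and s = 0.7: 0.6931/1.0498 × 0.65 = 0.429, so E = 2,575. In each cell the first value takes the incidence as pooled and the second as the comparator arm's.

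| s | HR 0.85: events; power % | HR 0.90: events; power % | Severe HR 0.80: events; power % |
|---|---|---|---|
| 1.0 | 3,000 / 2,836; 99.4 / 99.1 | 3,000 / 2,892; 82.3 / 80.9 | 900 / 816; 91.7 / 89.0 |
| 0.7 | 2,575 / 2,430; 98.5 / 98.0 | 2,575 / 2,480; 76.2 / 74.7 | 761 / 689; 86.8 / 83.4 |
| 0.5 | 2,250 / 2,121; 97.1 / 96.3 | 2,250 / 2,165; 70.5 / 68.8 | 655 / 593; 81.5 / 77.6 |
| 0.3 | 1,863 / 1,753; 93.9 / 92.5 | 1,863 / 1,791; 62.3 / 60.6 | 532 / 481; 73.0 / 68.7 |

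This model lets censoring start at day 0. If the first 60 days always count, the comparator-arm values at s = 0.7, 0.5 and 0.3 rise to 76%, 72% and 66% for HR 0.90, and to 84%, 80% and 74% for severe HR 0.80.

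**4. Slack in each figure.** On the pooled reading, the severe power falls below 90% under 845 events, which is about 12% off treatment at one year. HR 0.85 keeps 97% down to about 2,235 events, roughly half off treatment.

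**5. Larger sample.** With 4,000 per arm and s = 0.7, pooled, the powers are 99.8% (HR 0.85), 87.0% (HR 0.90) and 94.4% (severe HR 0.80).

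**The case against.** The strongest reply has four parts.

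First, the documents give no stopping or switching rate, so a reader who infers that all three stated powers are missed goes beyond them. That stands. HR 0.85 is hardly affected over a wide range of persistence. The 92% for severe exacerbations reproduces if 15% is pooled. The readable text also does not specify a separate model for severe exacerbations, so carrying the same censoring over to them is an inference.

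Second, 3,000 is called a minimum, and Section 7.7 says "we expect around 4,000 who received a LABA and tiotropium on the same day", a figure drawn from 2002–2012 users although entry runs to the end of 2015. More matched patients would offset some of the loss, and at 4,000 per arm with 70% persistence the first and third powers are restored. HR 0.90 still reaches only about 87%, and the stated powers are tied to 3,000.

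Third, a reader might infer that the event rates are inflated because they come from selected trial patients. Only the 50% is attributed to a trial. Section 5 describes the trials in general terms, "with several exclusion criteria involving for example stage of disease, lung function and exacerbation history", and does not say that this raised incidence. Any prednisolone prescription counts as an event here, which could push incidence up. A lower incidence is possible but is not shown.

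Fourth, readers will judge the result from its confidence interval, and the cohort is fixed by existing data. This limits the harm, but it does not make the stated power correct.

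**Conclusion.** The concern holds in a limited form. The 97% for HR 0.90 is wrong on the plan's own inputs: the Cox analysis has about 81–82% with complete follow-up, a gap of about 15–16 points. Censoring is not the main cause. A ratio of one-year risks has been labelled as a hazard ratio.

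Separately, Section 7.7 leaves out the censoring that Sections 7.3 and 7.9.1 impose. At 70% and 50% persistence this takes HR 0.90 to about 75–76% and 69–71%, and severe HR 0.80 to about 83–87% and 78–81% if it is analysed in the same way. HR 0.85 stays at about 96–98% and is not materially affected.

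These figures assume two-sided 5%, 3,000 per arm, proportional and exponential hazards, and non-informative exponential censoring. The persistence values are illustrations, not estimates. The error at HR 0.90 needs none of the censoring assumptions.

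**What to change.** Restate Section 7.7 as follows.

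- Give alpha, sidedness and the power formula.
- Correct the HR 0.90 power to about 81–82% before censoring.
- Say whether 50% and 15% are pooled or comparator-arm incidences, and name the source of the 15%.
- Say whether severe exacerbations will be analysed with the same as-treated model.
- Give expected as-treated events, power, and the HR detectable with 80% power over an assumed range of one-year persistence, such as 30–70%. With pooled incidence and 3,000 per arm, the detectable HR for the primary outcome is exp(−2 × 2.802/√E): 0.903 at 3,000 events, 0.895 at 2,575, 0.889 at 2,250 and 0.878 at 1,863.

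The cost is text only. The stated powers become less favourable. No extra patients and no change to the analysis are needed.

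### Section 7.7 claims 97% power at a hazard ratio of 0.90; on the hazard-ratio scale of the planned Cox analysis the stated inputs give about 81%

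*Combined protocol and SAP*

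**What the plan says.** All the power statements are in Section 7.7 (Study size). After matching and trimming, the sponsor expects "a minimum of 3,000 patients per arm, a conservative estimate". This comes from "around 4,000 who received a LABA and tiotropium on the same day" and a much larger pool of LABA-ICS users. The cumulative incidence of a first moderate or severe exacerbation "during the one-year follow-up is expected to be 50" per cent. The section does not say whether this refers to one arm or to both together.

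Three power figures follow from these sample sizes:

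- 99% for a 15% reduction in the risk of a first exacerbation (hazard ratio 0.85);
- "a 10% reduction (hazard ratio 0.90) with 97% power";
- for severe exacerbations, with a one-year incidence of about 15%, "a 20% reduction in the risk of a first severe exacerbation (hazard ratio 0.80) with 92% power".

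Section 7.7 gives no alpha, sidedness, test or formula, and makes no allowance for censoring. Section 7.9.1 (Main analysis) specifies a time-dependent Cox model, run as-treated, that estimates the hazard ratio of LABA-TIO against LABA-ICS with a 95% confidence interval. That analysis "censors patients stopping one or both of the drugs prior to the index date".

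**The concern.** The label attached to the figure and the planned estimate are both hazard ratios, so the power should follow from the expected number of events and the log hazard ratio. With 6,000 patients and about half having an event, there are about 3,000 events. That is far too few for 97% power at a hazard ratio as close to 1 as 0.90.

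Section 7.7 is the protocol's only statement of how sensitive the study is. Readers who take it at face value will believe that a true 10% reduction in hazard would be missed 3 times in 100. A null result would then look like stronger evidence against an effect of that size than the design can supply.

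**Working it through.** **Inputs.** From 7.7: 3,000 per arm, one-year incidence 50% (any exacerbation) or 15% (severe), hazard ratios 0.85, 0.90 and 0.80. From 7.3: one matched comparator per LABA-TIO subject (1:1) and follow-up of up to one year. Assumed: two-sided 5%, inferred from the 95% interval in 7.9.1; complete one-year follow-up; proportional hazards.

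**1. Reproducing the stated 97%.** Treat 0.90 as a ratio of one-year risks, so 50% against 45%, and compare two proportions with n = 3,000 per arm.

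- Standard error under the null: √(2 × 0.475 × 0.525 / 3000) = 0.01289.
- Standard error under the alternative: √((0.50 × 0.50 + 0.45 × 0.55) / 3000) = 0.01288.
- Power = Φ((0.05 − 1.96 × 0.01289) / 0.01288) = Φ(1.92) = **97.3%**.

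The same method gives 99.99% for 50% against 42.5% (stated 99%) and 92.5% for 15% against 12% (stated 92%). Under proportional hazards, 50% against 45% is a hazard ratio of ln(0.55)/ln(0.50) = **0.862**, not 0.90.

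**2. Power at a hazard ratio of 0.90.** Schoenfeld's formula for 1:1 groups with D events is power = Φ(√(D/4) × |ln HR| − z), with |ln 0.90| = 0.1054 and z = 1.96 (two-sided) or 1.645 (one-sided).

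If 50% is the LABA-ICS incidence, the LABA-TIO incidence is 1 − 0.5^0.9 = 46.4%. Then D = 3000 × 0.500 + 3000 × 0.464 = 2,892, and power = Φ(26.89 × 0.1054 − 1.96) = Φ(0.873) = 80.9%. The three possible readings of the 50% are:

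| 50% refers to | Events | Two-sided 5% | One-sided 5% |
|---|---|---|---|
| LABA-ICS arm | 2,892 | 80.9% | 88.3% |
| Both arms together | 3,000 | 82.3% | 89.3% |
| LABA-TIO arm | 3,111 | 83.6% | 90.2% |

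A log-rank simulation of the first row (exponential times, censoring at one year, 4,000 runs) gave 79.8%.

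**3. What 97% would need.** D = 4 × (1.960 + 1.881)² / (ln 0.90)² = 5,315 events, two-sided. That is 5,315 / 6,000 = 89% of the patients, against the stated 50%. At 0.500 + 0.464 = 0.964 events per matched pair it is about 5,500 patients per arm. With 3,000 per arm, the hazard ratio detectable with 97% power is 0.866.

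**4. A larger cohort.** If all of the roughly 4,000 LABA-TIO users expected before matching were matched, D = 3,856, 4,000 or 4,148 under the three readings. Two-sided power is then 90.5%, 91.5% or 92.4%; one-sided it is 94.8%, 95.4% or 96.0%.

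**5. The other two figures on the hazard-ratio scale (two-sided).**

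| Target | Stated | Incidence refers to LABA-ICS | Both arms | LABA-TIO |
|---|---|---|---|---|
| HR 0.85, 50% | 99% | 99.1% (2,836 events) | 99.4% (3,000) | 99.6% (3,173) |
| HR 0.80, 15% severe | 92% | 89.0% (816) | 91.7% (900) | 94.2% (1,002) |

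The 99% stands under every reading. The 92% stands if 15% is the overall incidence.

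**The case against.** The strongest reply is that 7.7 speaks first of a reduction in the risk of a first exacerbation, takes a one-year cumulative incidence as its input, and puts the hazard ratio only in brackets. Read as a risk reduction from 50% to 45%, 97% is correct. This stands: the fault is a confusion of two scales rather than a slip in calculation. But it makes the bracketed hazard ratio of 0.90 wrong, and that is the measure the primary analysis reports, so the sentence needs correcting either way.

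The two-proportion origin is also not proven. The two companion figures fit an event-based calculation with overall incidence (99.4% and 91.7%) at least as well, so the 97% could be an isolated slip. That is fair, and the conclusion does not depend on the origin.

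The 4,000 in 7.7 comes from a count of users between 2002 and 2012, whereas cohort entry runs to the end of 2015. Scaling by calendar years, which is an assumption, gives 4,000 × 14/11 = 5,091 before matching. If all were matched, power at 0.90 would be about 96% to 97% two-sided and 98% or more one-sided. A much larger cohort than planned could therefore come close. It does not rescue the text, which ties its figures to the 3,000 per arm that it calls a conservative minimum.

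Finally, the study uses all eligible existing records, and 81% still clears the customary 80%. Nothing in the design or the confidence intervals would change. This limits the consequence but does not make the figure right.

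**Conclusion.** The concern holds. At a hazard ratio of 0.90, with 3,000 per arm and 50% one-year incidence, power is about 81% (81% to 84% depending on which arm the 50% describes), not 97%. The type II error is therefore about 16% to 19%, where the plan implies 3%. This rests on a two-sided 5% test, proportional hazards and complete one-year follow-up. A one-sided test raises power to at most 90%, so sidedness does not explain the gap.

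If the 50% is a full-year incidence, as-treated censoring would lower the number of events and the power further. The documents give no discontinuation rate from which to say by how much.

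The figure for 0.85 is sound, and the one for severe exacerbations is sound if 15% is the overall incidence. The error overstates the study's sensitivity to the smaller target effect. No decision rule depends on it, but it should be fixed.

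**What to change.** In Section 7.7, use one scale for all three figures. The hazard-ratio scale is preferable because it matches the primary analysis:

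- if 50% and 15% are LABA-ICS incidences: about 99% (HR 0.85), 81% (HR 0.90) and 89% (severe, HR 0.80);
- if they are overall incidences: about 99%, 82% and 92%.

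Alternatively, keep 97% but describe it as power for a fall in one-year cumulative incidence from 50% to 45%, equivalent to a hazard ratio of about 0.86. The other two figures should then also be given as risk comparisons (50% against 42.5%, and 15% against 12%), so that the paragraph does not mix scales.

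In either case, state alpha, sidedness, the formula, which arm the 50% and 15% refer to, and that complete one-year follow-up is assumed. Power for the as-treated analysis under a labelled range of assumed persistence would be a useful but optional addition.

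The cost is a few sentences in one paragraph and, on the hazard-ratio scale, a less favourable figure at 0.90. Data, design and analysis do not change.

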7.8 DATA MANAGEMENT

All data related to this study will be stored on secured and encrypted database servers of the Data Management Unit Datacentre, located in the Centre for Clinical Epidemiology, Lady Davis Institute for Medical Research of the Jewish General Hospital, Montreal. The Centre for Clinical Epidemiology is equipped with an electronic access card system which is limited to the research staff and students of the Centre. The DMU Datacentre has a unique electronic access card system which is limited to specific personnel only. The building is under 24/7 video surveillance and regular scheduled round trips by security guards are done. The DMU Datacentre is monitored and managed for data access, data integrity and backup. The DMU Datacentre uses proven technology to safeguard its data, including Cisco ASA firewalls, IDS/IPS, antivirus, anti-spyware, hard drive encrypted, user access tracking, backup of all data. Copies of backed up files are kept in a safe outside of the institution.

All statistical analyses for the study will be conducted using SAS, Version 9.4 (SAS institute, Inc., Cary, NC) and R (R Foundation for Statistical Computing, Vienna, Austria; <http://www.R-project.org/>). All programs written by the statistical programmer, coding of variables, outputs and protocol amendments are stored in the servers. Access to the files related to a study is password-protected on the server and accessible only to the study statisticians. For ethical and scientific reasons, data and documentation are kept for five years following the publication date.

